## 9.2 Biostatistical methods

The two ARO-HBV analytes, JNJ 73763976 (AD04872) and JNJ 73763924 (AD05070) will be analyzed and presented separately (as appropriate).

ARO-HBV plasma concentrations will be listed by subject, dose level/treatment, and nominal (scheduled) sampling time. ARO-HBV concentrations will be summarized by dose level/treatment and nominal sampling time for the PK Analysis Population. Plasma concentrations that are below the limit of quantitation (BLQ) will be set to 0 for calculation of summary statistics for concentration data at each time point, except geometric statistics (geometric mean and geometric CV%). For the calculation of the geometric statistics they will be treated as equal to the Lower Limit of Quantification (LLQ). Missing values will be omitted from the calculation of descriptive statistics.

The actual blood sampling dates and times relative to dosing time will be listed by study group (dose level/treatment), subject and nominal sampling time, with time deviation calculated, for all subjects with available plasma concentration data, including subjects receiving placebo or subjects excluded from the PK Analysis Population.

Figures of individual plasma concentration vs. actual time profiles for ARO-HBV will be produced on both linear and semi-log scales for the PK Analysis Population. Mean and median plasma blood concentration vs. nominal time curves for all dose levels/treatments in the PK Analysis Population will be plotted together on both linear and semi-log scales for ARO-HBV.

Pharmacokinetic parameters for each dose level will be calculated from the concentrations of ARO-HBV measured in pre-dose and post-dose plasma samples. For the calculation of the PK parameters, all plasma concentrations that are BLQ prior to the first measurable concentration will be set to zero. The BLQ values that are between measurable concentrations will be set to missing. The BLQ values that occur at the end of the profile (after the last quantifiable concentration) will be set to missing and will not be used for the estimation of parameter values. Dose normalized PK parameters (DN\_AUC0-24, DN\_AUC0-inf, DN\_AUC0-t, and DN\_Cmax) will be calculated as well.

For each dose level, descriptive statistics will be provided for the PK parameters. Summary tabulations will display the number of observations, mean, SD, CV%, median, minimum and maximum. Geometric means and geometric CV% will be calculated for AUCs and Cmax. PK parameters will be displayed by treatment. AUC0-24, AUC0-inf, AUC0-t, and Cmax will also be presented in scatter plots by treatment.

The dose proportionality of ARO-HBV over the dose range 35–400 mg (NHV Cohorts 1-5) will be assessed by fitting a simple unweighted linear regression model with the natural log-transformed pharmacokinetic parameters (AUC0-24, AUC0-t, and Cmax) and dependent and the natural log-transformed dose values as independent variables.

Dose proportionality will be declared if the 95% CI for the slope of the regression line ( $\beta_1$ ) contains the value 1.  $AUC_{0-24}$ ,  $AUC_{0-t}$ , and  $C_{max}$  will be assessed separately.

The CHB Cohort 12 ARO-HBV, NUC and JNJ-6379 concentrations data will be summarized and presented graphically. The data will also be listed. PK parameters will not be calculated for Cohort 12.

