Plasma concentrations of ARO-HBV product constituents will be used to calculate the following PK parameters: maximum observed plasma concentration (C_{max}), area under the plasma concentration time curve (AUC) from time 0 to 24 hours (AUC_{0-24}), AUC from time 0 extrapolated to infinity (AUC_{inf}), and terminal elimination half-life ($t_{1/2}$). Pharmacokinetic parameters will be determined using non-compartmental methods. Descriptive statistics of PK parameters will include mean, standard deviation (SD), coefficient of variation, median, minimum, and maximum. PK results will be analyzed for dose proportionality, and sex differences.

Plasma concentrations of ARO-HBV, NUC and JNJ-6379 will be measured at a single post-dose time point in Cohort 12 only.

PK population: All NHV subjects and Cohort 12 patients that received at least one dose of active study treatment (ARO-HBV).

Genetic Testing (CHB patients only):

Evaluate mean and maximum nadir HBsAg decline in relationship to patient variants in interferon response genes (e.g. IL28B).

Pharmacodynamics:

Pharmacodynamic results, percent change, and duration of response from baseline to 24 hours post-dose will be analyzed and summarized by cohort and number of doses administered.

Immunogenicity (Anti-Drug Antibodies):

Changes from assay negative to positive will be summarized by dose and number of doses administered. Descriptive statistics of immunogenicity parameters will include mean, SD, minimum, and maximum.

Additional details will be provided in the statistical analysis plan.

Table 1.1: Cohorts 1 through 5 (Healthy Volunteers):

Assessment	Screen (Days -60 to -1)	Day -1 Confine		Day 1	Day 2 Discharge	Day 3	Day 8	Day 15 (± 2)	Day 29 (± 2) EOS	Early Termination
Informed Consent	X		RANDOMIZE							
Eligibility Criteria	X	X								
Body Mass Index	X									
Demographics	X									
Medical History	X	X*								
Drug Screen	X									
Hepatitis/HIV Serology Screen	X									
Physical Exam ¹	X	X*			X ¹	X ¹	X ¹	X ¹	X	X ¹
FSH	X ¹¹									
Pregnancy test	X ⁸				X ¹²				X	X
ECG	X				X ²	X		X	X	X
Vital Signs (BP, temp, RR, heart rate)	X				X ⁶	X	X	X	X	X
Clinical Labs (heme, coag, chem, UA)	X				X ¹⁰	X	X	X	X	X
PK ³					X	X	X			
Metabolite ID ¹³					X	X	X			
Urine collection for excretion and metabolite ID ¹⁴					X	X		X	X	X
Cytokines (Panel A) ⁴					X	X				
Complement ⁵					X	X				
Concomitant Meds/Therapies	X	X			X	X	X	X	X	X
Meals ⁷					X	X				
Adverse Events ⁹		X		X	X	X	X	X	X	
Study Treatment				X						

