## **2.4 Sample Size**

No formal statistical calculation of sample size will be used for this Phase 1/2a study. The sample size is empirical. The small numbers per cohort in this study are not intended for statistical hypothesis inference analysis. Results from this study will be utilized in sample size calculations for subsequent studies.

This study will involve approximately 30 eligible normal healthy volunteers in NHV cohorts and a minimum of 60 and a maximum of 84 CHB patients in CHB cohorts. Each of the 5 NHV cohorts will recruit 6 healthy volunteers. CHB cohorts 1b, 1c, 2b, 3b, 4b and 5b will recruit a minimum of 4 and a maximum of 8 patients, and CHB cohorts 6, 7, 8, 9, 10, 11 will recruit a maximum of 4 CHB patients. Cohort 12 will recruit 12 CHB patients.

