##### *Pharmacokinetic (PK) Population*

Subjects who have received the active treatment (ARO-HBV) and have adequate PK data to characterize PK profile will be included in the PK Population. This includes NHV Cohorts 1, 2, 3, 4 and 5 and CHB Cohort 12 subjects that received at least one dose of active study treatment (ARO-HBV).

Subjects who prematurely discontinue from the study will be included in the Safety Population but may not be included in the PK Population if they do not have PK data to contribute to the analyses. Subjects with missing sample concentrations will be included in the PK analyses provided their PK parameters can be adequately characterized based upon the remaining data. Subjects who received only placebo will be excluded from the PK population. The PK population will be used for the summaries of all PK data.

Subjects with protocol violations will be assessed on a subject-by-subject basis for inclusion in the PK Population. The determination of study populations will be made, prior to unblinding the PK data, at the blinded data review meeting before the final analyses for NHV Cohorts 1, 2, 3, 4, 5, and 12.

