### 9.1 Definition of variables

Whenever possible, the PK parameters listed below will be calculated for each subject based on the plasma concentrations of ARO-HBV according to the model independent approach, at Day 1.

Parameter	Description
AUC 0-24	The area under the plasma concentration-time curve, from time 0 (time of dosing) to 24 hours post dose, i.e., partial AUC, calculated by the log-linear trapezoidal method. AUCs for other time period could also be calculated in the analysis time.
AUC 0-inf	The area under the plasma concentration-time curve from time 0 extrapolated to infinity. AUC 0-inf is calculated as the sum of AUC 0-t plus the ratio of the last measurable plasma concentration to the elimination rate constant ( $\lambda_z$ ).
AUC 0-t	The area under the plasma concentration-time curve, from time 0 (time of dosing) to the last time point with measurable analyte concentration, calculated by the log-linear trapezoidal method.
C max	Maximum observed concentration.
T max	The first time when C max is observed
t ½	Apparent terminal elimination half-life of medication, calculated as 0.693/ $\lambda_z$ .
$\lambda_z$ :	The apparent first-order terminal elimination rate constant, calculated by linear least-squares regression analysis the terminal log-linear phase of the plasma concentration vs. time curves using at least 3 time points.
DN_AUC 0-24	Dose-normalized AUC 0-14d , calculated as AUC 0-t divided by dose

Parameter	Description
DN_AUC 0-inf	Dose-normalized AUC 0-inf , calculated as AUC 0-inf divided by dose
DN_AUC 0-t	Dose-normalized AUC 0-t , calculated as AUC 0-t divided by dose
DN_C max	Dose-normalized C max , calculated as C max divided by dose

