**16. CHANGES TO THE PLANNED ANALYSIS**

Any changes to the analyses outlined in the approved SAP will be detailed in the Clinical Study Report (CSR).

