### **17.2 Interim Analyses**

An interim analysis of the safety and PD data was planned and performed in May 2019 (data cut-off 27Mar2019). This interim analysis was conducted to assist with the planning of future studies and Health Authority interactions and did not impact the conduct of this study. The Sponsor was unblinded to selected summary data only.

A second interim analysis based on all study data up to Day 113 for all cohorts, was completed in February 2020 (data cut-off 14Nov2019).

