## 19. TABLES

Tables will be produced separately for NHV cohorts (Cohorts 1, 2, 3, 4 and 5), CHB cohorts (Cohorts 1b, 1c, 2b, 3b, 4b, 5b, 6, 7, 8, 9, 10, 11 and 12), and the subset of CHB patients that participated in the follow up period.

No.	Title	Analysis Population	Day 113: Interim Analysis
14.1.1.1	Summary of Disposition	Safety	X
14.1.1.2	Summary of Demographics	Safety	X
14.1.1.3.1	Summary of Baseline Disease Characteristics	Safety	X
14.1.1.3.2	Summary of Baseline Virology Characteristics	PD	X
14.2.1.1	Summary of Plasma Concentrations of ARO-HBV (ng/mL) by Dose [NHV Cohorts 1, 2, 3, 4 and 5 only]	PK	X
14.2.2.1	Summary of Plasma Pharmacokinetic Parameters of ARO-HBV by Dose [NHV Cohorts 1, 2, 3, 4 and 5 only]	PK	X
14.2.2.2	Analysis of Dose Proportionality for ARO-HBV [NHV Cohorts 1, 2, 3, 4 and 5 only]	PK	X
14.2.3.1	Summary of Plasma Concentrations of ARO-HBV (ng/mL), Nucleos(t)ide and JNJ-6397 Plasma Concentrations (Cohort 12) [CHB Cohort 12 only]	PK	
14.2.4.1	Summary of Anti-drug Antibodies [CHB cohorts only]	Safety	
14.2.4.2.1	Summary of Quantitative HBV Assessments and Change from Baseline [CHB cohorts only]	PD	X
14.2.4.2.1.1	Summary of Quantitative HBV Assessments and Change from Baseline by Baseline HBV DNA Group [CHB cohorts only]	PD	X
14.2.4.2.1.2	Summary of Quantitative HBV Assessments and Change from Baseline by Baseline HBeAg Group [CHB cohorts only]	PD	X
14.2.4.2.2	Summary of Quantitative HBsAg (IU/mL) by IL28B Genotype and Change from Baseline [CHB cohorts only]	PD	
14.2.4.2.3	Summary of Quantitative HBV Assessments Change from Baseline Categories [CHB cohorts only]	PD	X
14.2.4.2.4	Summary of Qualitative HBV Assessments [CHB cohorts only]	PD	X
14.2.4.3	Summary of HBV Virology Response [CHB cohorts only]	PD	X
14.2.4.4	Summary of Time to HBsAg Loss [CHB cohorts only]	PD	X
14.2.4.5	Summary of Time to Anti-HBsAg Seroconversion [CHB cohorts only]	PD	X
14.2.4.6	Summary of Duration of Response for HBV DNA [CHB cohorts only]	PD	X
14.2.4.7	Summary of Duration of Response for HBsAg	PD	X

No.	Title	Analysis Population	Day 113: Interim Analysis
	[CHB cohorts only]		
14.2.4.8	Summary of Duration of Response for HBeAg [CHB cohorts only]	PD	X
14.2.4.9	Summary of Duration of Response for HBcrAg [CHB cohorts only]	PD	X
14.2.4.10	Summary of Duration of Response for HBV RNA [CHB cohorts only]	PD	X

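### SAP 9.2 declares dose proportionality whenever the slope's 95% CI contains 1: a non-significant test is read as proof, and for any true slope other than 1, imprecise data make the declaration more likely

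*SAP*

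**What the plan says.** SAP 9.2 fits an unweighted linear regression of the natural log of AUC0-24, AUC0-t and Cmax, each separately, on the natural log of dose in NHV Cohorts 1–5 (35–400 mg). The decision rule is: "Dose proportionality will be declared if the 95% CI for the slope of the regression line" includes 1. SAP 3 makes intervals two-sided at 95% by default. SAP 9.2 also has the two ARO-HBV analytes analysed and presented separately as appropriate, so up to 3 × 2 = 6 such verdicts are possible.

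Neither document gives an equivalence margin, a precision requirement or a power statement for this rule. On sample size, SAP 2.4 says: "The small numbers per cohort in this study are not intended for statistical hypothesis inference analysis". The protocol synopsis says only "PK results will be analyzed for dose proportionality, and sex differences", and Protocol 11.5 adds that dose-related trends will be assessed. Neither protocol section sets a criterion for declaring proportionality.

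**The concern.** A two-sided 95% CI that contains 1 means only that a 5% test did not reject slope = 1. It shows that the data are compatible with proportionality, not that material departures have been excluded. For any slope estimate other than 1, widening the interval can only move the verdict towards proportional, so the rule rewards poor precision.

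Single-dose PK in healthy volunteers is one of two secondary objectives. The study report could therefore state that exposure is dose proportional when the data were merely too imprecise to show otherwise. A yes/no test verdict also sits badly with the statement in SAP 2.4 that the small cohorts are not meant for hypothesis inference.

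**Working it through.** The plan gives no figure to reproduce for this analysis, so the check derives how the rule behaves under the planned design.

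**Inputs from the documents**
- Doses: 35, 100, 200, 300 and 400 mg (SAP 2.1).
- Active subjects: 4 per cohort (SAP 2.5), so n = 4 × 5 = 20 at most, with 18 residual df.
- Rule: two-sided 95% CI for the slope contains 1 (SAP 3 and 9.2).

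**Assumptions, not in the documents**
- Between-subject CV of 20, 30, 40, 50 or 80%.
- True slopes of 1.2 and 1.3 as example departures.

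**Spread of log dose.** ln(dose) = 3.555, 4.605, 5.298, 5.704, 5.991, with mean 5.031. The squared deviations sum to 3.806, so Sxx = 4 × 3.806 = 15.22. With 3 evaluable subjects per dose, Sxx = 11.42.

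**What a slope means.** The dose ratio is 400/35 = 11.43, and ln(11.43) = 2.436. The departure from proportional exposure across the range is exp[(slope − 1) × 2.436]. A slope of 1.2 gives 1.63-fold, 1.3 gives 2.08-fold and 0.7 gives 0.48-fold.

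**Formulas**
- σ = √ln(1 + CV²); SE = σ/√Sxx.
- 95% half-width = t × SE, with t(0.975, 18) = 2.101, or t(0.975, 13) = 2.160 for 15 subjects.
- Half-width expressed as a factor on the 400 vs 35 mg dose-normalised ratio = exp(half-width × 2.436).
- Probability of declaring = P(|T| < t), where T is noncentral t with noncentrality (slope − 1)/SE.

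| CV | σ | SE (n = 20) | Slope half-width | Factor on ratio | Declared, slope 1.2, n = 20 | Declared, slope 1.3, n = 20 | Declared, slope 1.3, n = 15 |
|---|---|---|---|---|---|---|---|
| 20% | 0.198 | 0.051 | 0.11 | 1.30 | 4% | 0.02% | 0.3% |
| 30% | 0.294 | 0.075 | 0.16 | 1.47 | 29% | 3.5% | 11% |
| 40% | 0.385 | 0.099 | 0.21 | 1.66 | 52% | 18% | 32% |
| 50% | 0.472 | 0.121 | 0.25 | 1.86 | 65% | 35% | 49% |
| 80% | 0.703 | 0.180 | 0.38 | 2.52 | 82% | 65% | 73% |

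Slopes of 0.8 and 0.7 give the same rates as 1.2 and 1.3. A true slope of exactly 1 is declared 95% of the time at every CV. Simulating the slope-1.3 case with n = 20 (200,000 trials) gave 0.02 / 3.5 / 18.1 / 35.0 / 65.0%, in agreement with the table.

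At CV 80% the verdict therefore separates slope 1 from slope 1.3 only as 95% against 65%. At every CV, losing data raises the rate of false declaration.

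**The case against.** - **Assumed inputs.** The CVs and the example slopes are choices, not plan figures. At slope 1.3 the false-declaration rate is 0.02% at CV 20% and 3.5% at CV 30%. This stands as a limit on the size of the problem; the direction does not depend on CV.
- **SAP 2.4 concerns numbers per cohort.** The regression pools up to 20 subjects across five cohorts, and the SAP uses 95% CIs elsewhere for virology responses and time-to-event endpoints. That is fair: the tension comes from the declaration, not from computing an interval.
- **The protocol invites formal analysis.** Protocol 11.5 calls for dose-related trends and statistical analysis of the PK parameters, so the regression is a legitimate elaboration. It still supplies no basis for a declaration.
- **Fifteen subjects may be pessimistic.** The SAP says subjects who discontinue early "may not be included in the PK Population if they do not have PK data to contribute to the analyses", but it keeps those with missing samples if their parameters can be characterised. The protocol synopsis also allows replacement of healthy volunteers who withdraw before the last PK sample for reasons other than an adverse event. Replacement is optional, so the scenario is possible, but these provisions make it less likely.
- **Other displays would help.** Geometric means by dose and the raw and dose-normalised scatterplots would partly reveal a departure. They would not change the prespecified verdict.
- **Timing.** Table 14.2.2.2, "Analysis of Dose Proportionality for ARO-HBV", is marked for the Day 113 interim, and SAP 17.2 says: "A second interim analysis based on all study data up to Day 113 for all cohorts, was completed in February 2020". Dropping a criterion after results may have been seen is itself a change that needs disclosure. This stands as a cost.

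**Conclusion.** The concern holds. As written, SAP 9.2 turns non-rejection of slope = 1 into a conclusion of proportionality, and for any true slope other than 1 that conclusion becomes more likely as precision falls. If the slope is exactly 1, interval width does not matter.

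The size depends on the assumed CV and on the departure considered. For a 2.08-fold departure with 20 subjects, it runs from negligible at CV 20% to a 65% chance of a false declaration at CV 80%.

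The point is minor. Escalation is decided by the DSC on safety data (SAP 17.1), and nothing else in the trial depends on this verdict. What is at risk is a wrong written conclusion on a secondary objective.

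**What to change.** Delete the yes/no declaration from SAP 9.2. For AUC0-24, AUC0-t and Cmax, report the slope with its 95% CI and the implied dose-normalised exposure ratio (400/35)^(slope − 1) with its 95% CI, described as estimates consistent with SAP 2.4.

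Do not substitute a pass/fail margin. The documents give none, and choosing one after the completed interim would be hard to defend. As an illustration, requiring the 90% CI to lie within a 0.80–1.25 exposure ratio over the range means slope limits of 1 + ln(0.80)/2.436 = 0.908 to 1 + ln(1.25)/2.436 = 1.092. With 20 subjects and a true slope of exactly 1, this would be met about 13% of the time at CV 20% and 0.3% at CV 30% (200,000 simulated draws).

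Record the change, with its timing relative to the interim, under SAP 16: "Any changes to the analyses outlined in the approved SAP will be detailed in the Clinical Study Report". The cost is SAP wording and possibly the layout of Table 14.2.2.2, whose shell is not in the documents. The slope and CI are already computed. What is lost is a one-word verdict for each parameter and analyte, and the change has to be disclosed as made after the interim.

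Separately, correct a clerical slip in SAP 9.1 that does not affect the regression. The DN_AUC0-24 row reads "Dose-normalized AUC 0-14d , calculated as AUC 0-t divided by dose", the same formula as DN_AUC0-t, so Figures 14.2.4.1 and 14.2.4.3 would plot the same quantity. It should be AUC0-24 divided by dose.

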## **10. SAFETY**

Statistical methods for the safety analyses will be primarily descriptive in nature. Each dose level (cohort) will be summarized separately.

Safety endpoints included in the analysis are AEs, concomitant medications, clinical laboratory assessments, vital signs, physical examination, and 12-lead ECG.

Safety endpoints will be analyzed separately for the main study (up to Day 113 EOS) and for the overall study duration, including the follow-up period, for the subset of CHB patients that consented to participate in the follow-up. Endpoints will be derived separately for each analysis taking into consideration all the applicable data for the specific period.

Safety endpoints will be analyzed using the Safety Population.

### **10.1 Adverse Events**

Adverse events (AEs) will be coded using the Medical Dictionary for Regulatory Activities (MedDRA®, the latest available version), and data will be summarized by System Organ Class (SOC) and Preferred Term (PT). The number and percent of subjects reporting each AE will be summarized for each dose level (cohort) and overall. A subject with two or more AEs within the same level of summarization (i.e., SOC or PT) will be counted only once in that level. Percentages will be based on the number of subjects in the Safety Population within each dose level (cohort). The number of AEs reported will also be presented.

Treatment-emergent AEs (TEAEs) are defined as pre-treatment existing conditions that worsen after study drug administration, or events that occur during the course of the study during or after administration of study drug. Only TEAEs will be included in the AE summary tables which will present data by dose level (NHV/CHB cohorts) for active treatment versus pooled placebo subjects (NHV cohorts). In the case of a missing AE start date or stop date, the most conservative approach will be followed to classify AE into TEAE unless it is not possible that the AE could be treatment emergent. AEs that occurred during the follow-up period will only be included in the follow-up table.

A table providing an overall summary of AEs will be produced which will include the number of TEAEs; the number and % of subjects reporting at least one: TEAE, serious TEAE, grade 3 (severe) or higher TEAE, TEAE related to study treatment (related to ARO-HBV or JNJ-6379 [Cohort 12 only]: possibly/probably), serious TEAE related to study treatment, grade 3 or higher TEAE related to the study drug, TEAEs by severity and TEAEs by relationship, drug or study discontinuations due to TEAEs. The table will also be repeated for related (ARO-HBV or placebo) TEAEs.

Additional AE tables will be generated as follows:

- TEAEs by SOC and PT
- TEAEs by decreasing incidence of the PTs in the Combined ARO-HBV group
- Study Drug (ARO-HBV or placebo) Related TEAEs by SOC and PT
- Study Drug (ARO-HBV or placebo) Related TEAEs by decreasing incidence of the PTs in the Combined ARO-HBV group
- Study Drug (JNJ-6379) Related TEAEs by SOC and PT (Cohort 12 only)

- Study Drug (JNJ-6379) Related TEAEs by decreasing incidence of the PTs in the Combined ARO-HBV group (Cohort 12 only)
- TEAEs by Severity
- TEAEs by Relationship to Study Drug (ARO-HBV)
- Treatment Emergent SAEs
- Study Drug (ARO-HBV or placebo) Related SAEs by SOC and PT
- Study Drug (JNJ-6379) Related SAEs by SOC and PT (Cohort 12 only)
- TEAEs Leading to Study Drug or Study Withdrawn
- TEAEs occurring at the treatment injection site by SOC (General disorders and administration site conditions) and PT linked to High Level Term, "Injection Site Reaction"
- TEAEs fitting the definition of LISR by SOC and PT

A by-subject AE data listing, including verbatim term, MedDRA SOC and PT, severity, outcome and relationship to study treatment, will be provided. Separate listings will be generated for SAEs. AEs that started during the follow-up period will be flagged. Cohort 12 data will be listed separately.

Local Injection Site Reactions (LISR)

Local Injection Site Reactions will be reviewed based on description of symptoms, level of severity (mild, moderate or severe) and outcome of the reactions as well as other relevant data elements such as de/re-challenge, medical history, and possible confounding variables. Based on the review, the reactions will be specifically categorized and collated for the analysis.

The results will be summarised by cohort across all dose levels and percentages for the reported LISR by using the MedDRA coding system by System Organ Class (SOC), General disorders and administration site conditions and Preferred Terms that are associated with local injection site reactions.

The following MedDRA Preferred Terms determined by the Sponsor's pharmacovigilance personnel represent the local injection site reaction:

Injection site discomfort	Injection site abscess
Injection site discoloration	Injection site abscess sterile
Injection site erythema	Injection site atrophy
Injection site irritation	Injection site calcification
Injection site inflammation	Injection site cellulitis
Injection site induration	Injection site dermatitis
Injection site pain	Injection site erosion
Injection site oedema	Injection site fibrosis
Injection site pruritus	Injection site indentation
Injection site rash	Injection site necrosis
Injection site urticaria	Injection site nodule
Injection site reaction	Injection site ulcer
Injection site swelling	

Those summaries will only include events that start on the day of injection and persist for at least 2 days (48 hours) post injection (i.e., event onset date on the day of injection and

resolution date not on the day of injection or the day after the injection) will be included. Events with onset date on the day of injection and missing resolution date will also be included in the summary.

The percentage of injections leading to local injection site reactions will be summarized using descriptive statistics.

The following calculation will be utilized to determine the percentage of injections leading to local injection site reactions for each subject:

$(A/B) *$ , where A = number of injections with a local injection site reaction, and B = total number of injections.

The results of local injections site reactions will be provided in summary tabulation.

